## **5.2 Independent Ethics Committee / Institutional Review Board and Authorities**

### **IEC/ IRB**

According to applicable regulations, the appointed CRO or the Site Study Responsible will:

- notify or obtain approval from the relevant IEC/IRB of the protocol, any amendments and the Subject Information Sheet / Informed Consent Form

The appointed CRO or the Site Study Responsible will submit required documents to the IEC / IRB, such as:

- periodic updates on the progress of the study
- notification of the end-of-study
- a summary of the study results

Global Research will keep an updated list of all submission and approval dates of all documents submitted to the IEC / IRB and will provide the Site Responsible with a copy of this list. Copies of the documents will be distributed upon request.

### **Authorities**

Global Research or the appointed Contract Research Organisation (CRO) will send required documents to the competent authority (CA) and/or other national or regional authorities. Global Research will keep an updated list of submission and approval dates and a copy of all documents submitted.

Once the study has obtained classification from the AEMPS [Spanish Agency of Medicines and Medical Devices], approval by an IEC and the other administrative procedures have been completed, the study will commence at the participating sites.

### **5.3 Subject Information and Written Informed Consent**

This study will follow standards of good clinical practice (GCP) as they apply to epidemiological studies, thereby ensuring that its design and conduct and the communication of the data are reliable and protect the rights and integrity of the participating subjects and the confidentiality of their data.

Before starting the study, the protocol, patient information sheet and informed consent form for the study will be submitted for approval to the Independent Ethics Committee (IEC) of one hospital and to any of the IECs of any participating sites that request it. The sponsor will keep the IEC's favourable opinion, together with the versions of the documents approved and the list of members of the committee having issued the opinion.

Patients who meet the inclusion criteria and give their informed consent will be recruited to the pain characterisation study until the indicated sample size is reached. Each subject invited to participate in the pain characterisation study will be given a written document called a "Patient Information Sheet" that will contain the relevant and necessary information to enable him/her to decide whether to participate in the study.

The investigator must inform the patient as fully as possible, using language and terms that the latter can understand, about the voluntary nature of participation and that this will not entail any change to his/her treatment or medical care with regard to what he/she would receive if not participating. The investigator will respond to the patient's doubts and questions and, in accordance with current legislation, obtain the subject's written informed consent which must be signed by the subject (in his/her own hand with name and date) or, if not possible, that of an impartial witness, in which case he/she shall sign the verbal informed consent form before witnesses, or of the patient's legal representative. The patient will receive a signed and dated hard copy of the informed consent form, signed also by the investigator.

Subjects participating in the study may at any time withdraw their consent to the use of their data in the analysis, without giving a reason and without incurring any liability or loss.

The Site Study Responsible must give the subject (and if applicable, parent or legal guardian) oral and written information about the study in a form that the subject (, parent or legal guardian) can understand, and obtain the subject's (and if applicable, the subject's assent and the parent's or legal guardian's) written consent before collection of identifiable subject information (hereinafter referred to as personal data). Before consenting, the subject (and if applicable, parent or legal guardian) must be left with ample time to consider and to pose questions. Since the study is observational the consent only concerns the data collection per se and is not consent to any interventional procedure or treatment.

The subject must agree that sponsor personnel, their representatives or IEC/IRB or CA personnel (national or other) may require direct access to the subject's data / personal records which were collected, processed and stored in an anonymous form.

The subject must agree that his / her data will be processed and stored in an anonymous form for evaluation of this study and any later overviews. Data may also be transferred in anonymous form to third parties, e.g. other companies or authorities, that may be located in other countries with potentially different regulations for data.

The subject and parent or legal guardian, if applicable, has the right to withdraw his/her consent at any time without prejudice. In the Informed Consent Form it is stated that if consent is withdrawn, any data collected before withdrawal of consent will be kept. The original, signed Informed Consent Forms must be kept on the Site.

For details, see the Subject Information Sheet and Informed Consent Form.

#### **5.4 Risk–benefit analysis for research subjects.**

Due to its observational nature, there is no possibility of the study generating any risk whatsoever for the subjects studied as it does not entail any change in patient care with respect to normal clinical follow-up. The patient will not receive any benefit as a result of his/her participation in the study and will be treated in accordance with the participating physician's normal clinical practice. Nevertheless, this study may help to improve knowledge of the incidence and prevalence of patients with breakthrough cancer pain, as well as the characterisation of this type of pain, that can be incapacitating for the patient, which may enable improvements to be made in the care of such patients in normal clinical practice.

### **6 Study Design and Plan**

This study is a 'non-interventional study' as defined in: G-STND-PV-006, Pending SOP, Directive 2001/20/EC (4) and will follow the guidelines for GPP (2).

This means that:

- The assignment of a subject to a particular therapeutic strategy is not decided in advance by the study protocol but falls within current practice
- No additional diagnostic or monitoring procedures shall be applied to the subjects
- Epidemiological methods shall be used for the analysis of collected data.

This is a cross-sectional, non-PAS, non-interventional, epidemiological study. Given the observational and cross-sectional nature of the study, the protocol does not include any interventions with regard to patient follow-up by the investigator.

The proposed design is considered sufficient to enable the collection of the data required to meet the study's objectives.

## 6.1 Study Schedule

Start of recruitment:	September 2016
End of recruitment:	June 2017
Data collection:	3 months
Data analysis:	December 2017
Total duration of study:	15 months

The Start of Study is defined as date of first Site Initiation.

Global Research will ensure that End-of-Study notification is submitted to the concerned authorities and IEC/IRB for each site, for each country and for the complete study, as locally required.

Global Research will ensure that results are posted on “clinicaltrials.gov” and as required by local authorities.

Based on upcoming knowledge, Takeda might choose to terminate the study prematurely. In such case the Committee(s), study sites, IECs/IRBs and authorities will be informed promptly.

## 6.2 Discussion of Study Design

The study’s limitations derive from its design as a cross-sectional, non-PAS, non-interventional study in which the proportion of patients with breakthrough cancer pain attending consultations in Medical Oncology, Hematology, Radiotherapeutic Oncology Departments, Pain Units and Palliative Care Units may not be representative of the general population of cancer sufferers. However, it will allow us to obtain a valid estimate in the population attending said consultations.

A further limitation relates to the extrapolation of the results to the national population, as although 66 sites distributed throughout the country will participate in the study, it is possible that these may not be representative of Spain as a whole, due to the characteristics of the sites selected.

### 6.3 Selection of Study Population

Patients with cancer pain assessed in in Medical Oncology, Hematology, Radiotherapeutic Oncology Departments, Pain Units and Palliative Care Units at the hospitals participating in the study.

#### **Inclusion criteria:**

- Patient  $\geq$  18 years old
- Patients with baseline cancer pain that is adequately controlled with opioids
- Presence of episodes of breakthrough pain associated with the cancer pain
- Meeting the diagnostic criteria for breakthrough cancer pain (patient history and Portenoy's criteria) and the Davies algorithm
- Patients who are not receiving treatment for breakthrough cancer pain. It is not permitted the inclusion of patients receiving treatment for breakthrough cancer pain in order to avoid bias that may affect the characterisation or taxonomy of breakthrough cancer pain
- Signing of the informed consent

#### **Exclusion criteria:**

- Severe mental illness
- Any medical condition or situation complicating the collection of study data as determined by the investigator

The source of information will in all cases be the medical history, the patient and the questionnaires completed during the visit. In accordance with the study design, the investigator will collect the study variables and data in a single visit.

For a period of one month, each investigator must identify cancer patients who attend consultations in Medical Oncology, Hematology and Radiotherapeutic Oncology Departments or Pain and Palliative Care Units, using the Davies diagnostic algorithm [3] to confirm the presence of breakthrough pain. From those patients who report breakthrough pain, the first two patients each day who meet the inclusion criteria and give their informed consent for the characterisation of breakthrough pain will be recruited, until reaching 10 patients in Medical Oncology, Hematology, Radiotherapeutic Oncology and Palliative Care Departments and 5 patients in Pain Units. If an investigator has been unable to include the

expected number of patients planned for the characterization of breakthrough pain during the month that has collected prevalence data, the investigator will have two additional months to include them, and the investigator must confirm the presence of breakthrough pain by Davies algorithm before inclusion as detailed above.

Subjects should be included in the study only once.

Data erroneously collected from subjects for which written consent is not available, will not be included in the final analysis and will be deleted from the database. All relevant actions will be taken according to GCP standards and local legislation.

#### **6.4 Treatments**

The patients participating in this cross-sectional, non-PAS, non-interventional study will not receive treatment in relation to the study aside from the treatment already prescribed by their usual physician.

### **7 Conduct**

Once the study has obtained classification from the AEMPS [Spanish Agency of Medicines and Medical Devices], approval by an IEC and the other administrative procedures have been completed, the study will commence at the participating sites.

Data will be collected from patients with cancer pain being treated with third-step opioids who attend consultation at the in Medical Oncology, Hematology, Radiotherapeutic Oncology Departments, Pain Units and Palliative Care Units of participating sites during a period of 1 month. Each of the participating investigators must identify the patients with cancer pain and confirm the presence of breakthrough pain using the Davies diagnostic algorithm [3]. The investigator will propose participation in the study on the characterisation of breakthrough pain to the first two patients each day who meet the selection criteria. If the patient agree to participate in the study they will be asked to sign the informed consent. If any of the patients refuses to participate the enrolment will continue the next day. It is expected that each investigator in the Medical Oncology, Hematology, Radiotherapeutic Oncology and Palliative Care Departments will recruit 10 patients to the study and investigators in the Pain Units will recruit 5 patients due to the lower number of cancer patients in Pain Units. In

accordance with the study design, the investigator will collect the necessary variables and data in a single visit.

The fieldwork will take 1 month to collect prevalence data and maximum 3 months for the collection of data for the characterization of breakthrough pain, if the investigator could not recruit all foreseen patients for this purpose in the first month. First month corresponds to the recruitment period required for the incidence/prevalence calculation, as due to the study's characteristics no follow-up period is planned. Data entry in the database, analysis and the drafting of the final report will be carried out once the recruitment period is concluded.

As this is an observational, cross-sectional, non-PAS and non-interventional study, it will not under any circumstances involve changes to normal clinical practice or the performance of tests not considered normal clinical practice. Throughout the study, each investigator must treat the patients diagnosed with breakthrough cancer pain and recruited to the study, whether treatment-naïve or currently untreated, after characterising their pain, in accordance with the criteria habitually used in clinical practice for patients of this type.

The study period is initially estimated at 12 months for data collection. This corresponds to the recruitment and data entry periods, as due to the study's characteristics no follow-up period is planned. Data entry in the database, analysis and the drafting of the final report will be carried out once the recruitment period is concluded. If, following the recruitment period planned in the protocol (maximum 3 months), the expected number of patients for the characterisation of breakthrough pain has not been reached, recruitment will be continued competitively within each specialty (120 patients included in each specialty except 60 patients in hematology), until 529 patients have been recruited.

The investigator will be responsible for ensuring the correct completion of all sections of the Case Report Form.

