## 2 Introduction

Oncology consultations are generally short in duration (20-30 minutes). The primary consideration for most oncologists during this time is treatment of the tumour: the choice of treatment to be administered to the patient (chemotherapy, radiotherapy, etc.), the administration of recommended treatment, and the monitoring and control of the efficacy and safety of these treatments, principally in relation to tumour response and survival [4].

Symptoms, such as pain, are often given less attention during diagnosis and treatment. Pain is one of the most common symptoms of cancer [5-7]. However, published estimates of the prevalence of pain in outpatients are inconsistent and vary between 18% and 62%, probably due to differences between the various selection criteria, the use of dissimilar assessment tools and/or different tumour stages [5-7].

Breakthrough pain is understood as the temporary exacerbation of pain occurring either spontaneously or in relation to a specific, predictable or unpredictable trigger in spite of relatively stable and adequately controlled baseline pain.

Breakthrough cancer pain is a common and distressing subtype of pain that affects a percentage of patients with cancer that varies between 40% and 90% according to different publications [1, 2]. The type of breakthrough pain seen in cancer is described as “a temporary increase in pain with an intensity above that considered moderate, overlying baseline pain of moderate or low intensity” in cancer patients treated with opioids [8].

Breakthrough cancer pain is a high intensity, short duration pain that manifests in several daily episodes and does not respond to normal treatment. The clinical approach to breakthrough cancer pain is changeable. The data show that daily exacerbations of pain need to be monitored closely, differentiating where possible between fluctuations in baseline pain and the end-of-dose effect [9].

The causes of cancer breakthrough pain are the same as those of cancer pain, and they can be related to the neoplasm, with diagnostic tests, treatment or other concomitant problems concurrent with cancer [10]. In terms of physiology, breakthrough pain may be nociceptive, neuropathic or mixed [10].

Even today, clinical focus in breakthrough pain varies considerably between clinics, from complete denial of its existence to overestimation [9].

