### **3 Study Objective(s)**

#### **Primary objective**

- To estimate the prevalence of breakthrough cancer pain in an unselected representative cohort of cancer outpatients with or without pain who attend consultations at Medical Oncology, Hematology, Radiotherapeutic Oncology Departments, Pain Units and Palliative Care Units at participating sites. The estimated annual prevalence will be calculated relative to the population of cancer patients with or without pain seen in participating practices over one month.

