### **Description of the visit**

A single visit per patient will be carried out for the purposes of this study, coinciding with the study recruitment visit.

For a period of one month, each investigator must identify patients with cancer pain being treated with opioids who attend consultations in in Medical Oncology, Hematology, Radiotherapeutic Oncology Departments, Pain Units and Palliative Care Units, using the patient's medical history and the Davies diagnostic algorithm [3] to confirm the presence of breakthrough pain.

Information relating to the prevalence of breakthrough pain will be collected in the corresponding section of the CRF, detailing for each patient whether he/she has pain, whether he/she has breakthrough pain, age, sex, Karnofsky PS, tumour type and stage.

From those patients who report breakthrough pain, the first two patients each day who meet the inclusion criteria and give their informed consent will be recruited, until reaching the indicated sample size of 10 patients in Medical Oncology, Hematology, Radiotherapeutic Oncology and Palliative Care Departments and 5 patients in Pain Units, until a total of 529 is reached.

If, following the recruitment period planned in the protocol (maximum 3 months), the expected number of patients for the characterisation of breakthrough pain has not been reached, recruitment will be continued competitively within each specialty (120 patients included in each specialty except 60 patients in hematology), until 529 patients have been recruited.

The information will be recorded on the Case Report Forms (CRFs) designed for this purpose. All the information will be filled in by the investigating physician using the data obtained during the study visit or by checking the patient's medical records when necessary.

The following information will be collected during the visit:

- Visit date
- Demographic data (age, sex, weight, height)
- Characteristics of the cancer (type, stage, treatments the patient has received for the underlying tumour: chemotherapy, radiotherapy, surgery, etc.) as well as whether he/she is currently receiving treatment for the tumour.
- Comorbidities
- Adverse events associated with the cancer treatment or sequelae of the tumour: (mucositis, xerostomia, nausea, vomiting, dysphagia, dyspnoea, peripheral neuropathy, tiredness/weakness, constipation, diarrhoea, sleep disorders, other)
- Clinical assessment of the breakthrough pain:

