### **9.5 Methods for obtaining data.**

This study entails the cross-sectional collection of data over one month at each participating site. Given the observational nature of the study, the data will be obtained in a single visit from patients' medical history and/or from the patient using the tools detailed above and in accordance with the physician's normal clinical practice.

The presence of breakthrough pain and its characterisation will be assessed using the questionnaires detailed in section H4 of the protocol in those patients who agree to participate in the study by signing the informed consent.

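### The protocol gives sites conflicting rules on who enters the one-month prevalence register, and its narrower rules leave out patients whom the primary objective counts

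*Protocol*

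**What the plan says.** The primary objective (Protocol, Section 3; repeated in SAP, Section 3.5) concerns an "unselected representative cohort of cancer outpatients with or without pain who attend consultations", and adds: "The estimated annual prevalence will be calculated relative to the population of cancer patients with or without pain seen in participating practices over one month".

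The instructions on whom to identify or record differ:

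- **Section 6.3** opens by describing the study population as patients with cancer pain. After the exclusion criteria it says "each investigator must identify cancer patients who attend consultations in Medical Oncology, Hematology and Radiotherapeutic Oncology Departments" or the pain and palliative units, with no pain or opioid condition.
- **Section 7, Conduct:** "Data will be collected from patients with cancer pain being treated with third-step opioids who attend consultation". This is the only use of the third-step term. The next sentence speaks of patients with cancer pain, with no opioid condition.
- **Section 7, Description of the visit:** "each investigator must identify patients with cancer pain being treated with opioids who attend consultations". The same any-opioid wording recurs later in Section 7 and in Section 10.1.
- **Section 9.5:** "The presence of breakthrough pain and its characterisation will be assessed using the questionnaires detailed in section H4", which the sentence goes on to tie to patients who sign consent.

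Other text points to a wide register. The visit description has the CRF show, for each patient, whether pain is present. Sections 7 and 10.1 also call for prevalence relative to all cancer patients. SAP Section 5.1 lists cancer pain as a yes/no item, and SAP Section 5.2 gives a formula over all patients registered with cancer.

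The primary variable in Section 7 and the primary analysis in SAP Section 5.1 are set in opioid-controlled cancer pain. The SAP formula divides by patients registered with cancer pain. SAP Section 4.1 takes as the prevalence population everyone on the prevalence form.

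**The concern.** This is about who gets onto the register, which comes before any choice of formula. If pain-free attenders are not entered during the month, no later analysis can rebuild the all-cancer denominator. If some sites enter all attenders and others only pain patients, the SAP's count of patients registered with cancer mixes two populations. Differences between specialties would then partly reflect which paragraph a department followed.

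A filter on opioid use or step would also be invisible afterwards. The register variables (Section 7, Description of the visit; SAP Section 5.1) include no opioid item, so pain patients left out for their opioid step could not be detected.

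**Working it through.** **1. Who is left out under each rule, read literally**

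| Rule | Source | Left out, relative to the objective |
|---|---|---|
| Cancer patients | 6.3, after the exclusion criteria | nobody |
| Cancer pain | 6.3 opening; Section 7, sentence after the third-step one | pain-free patients |
| Cancer pain on opioids | Visit description; later in Section 7; 10.1 | the above, plus pain patients not on opioids |
| Cancer pain on third-step opioids | Section 7, Conduct | the above, plus pain patients on lower-step opioids |

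**2. The plan's own precision figure**

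Inputs from Protocol Section 10.3: 200 patients at each of 66 sites, prevalence 50%, 95% interval, stated precision ±1%.

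- 66 × 200 = 13,200.
- Half-width = 1.96 × √(0.5 × 0.5 / 13,200) = 0.85 points, so ±1% is met.
- ±1% needs 1.96² × 0.25 / 0.01² = 9,604 patients.

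This treats patients as independent, with no clustering by site. The count starts from patients attending for cancer, so it matches the wide register.

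**3. A site that enters only pain patients**

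Input: pain in 18% to 62% of outpatients (Protocol, Section 2).

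- Entered: 200 × 0.18 = 36 to 200 × 0.62 = 124.
- Every patient with breakthrough pain has pain, so the numerator is complete and only the denominator shrinks.
- Overstatement of that site's all-cancer prevalence: 1/0.62 = 1.61 to 1/0.18 = 5.56.

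**4. Study-wide range**

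- All sites read narrowly: 13,200 × 0.18 = 2,376 to 13,200 × 0.62 = 8,184 registered. Half-width at 50%: 1.96 × √(0.25/2,376) = 2.01 points to 1.96 × √(0.25/8,184) = 1.08 points. Both miss ±1%.
- Half of sites read narrowly (assumption: equal size, same pain share): 1/(0.5 + 0.5 × 0.62) = 1/0.81 = 1.23 to 1/(0.5 + 0.5 × 0.18) = 1/0.59 = 1.69.
- No sites read narrowly: factor 1.

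**5. Third-step limit**

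The documents do not give the share of pain patients on third-step opioids. Assuming 25% to 100%, between 13,200 × 0.18 × 0.25 = 594 and 8,184 patients remain, with half-widths of 4.02 to 1.08 points. This limit may also remove patients with breakthrough pain on lower-step opioids, so the factors in step 3 do not carry over to it.

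**The case against.** A reader might infer that Section 7 confines the register to third-step patients, so that the patients in the objective are never recorded. The documents do not support that. The sentence contains no word such as only. Patients with breakthrough pain on third-step opioids are recorded and belong to the objective's numerator and denominator. The pain field, the all-cancer prevalence in Sections 7 and 10.1, and the SAP's all-cancer formula all presuppose that pain-free patients are entered. These show intent, but they do not instruct a site to enter patients whom the Conduct text does not tell it to identify.

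Four further objections have force.

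- Section 6.3 is not a clean rule to fall back on: it opens with patients with cancer pain, and its wider sentence says identify, not register.
- Section 9.5 might be read as a further entry rule limited to consenting patients. That reading is weak, because Sections 5.3 and 7 tie consent to the characterisation part.
- Missing pain-free patients do not affect the SAP's primary formula, whose denominator is patients with cancer pain. They affect the all-cancer prevalence and the annual figure. So it goes too far to say that the primary analysis as coded fails.
- An opioid filter at entry is at present the only thing that makes the SAP's denominator of registered pain patients mean opioid-controlled pain. Widening the register without recording opioid control would make the primary variable uncomputable.

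A 1.6-fold factor is also not a minimum. The 18% to 62% range describes outpatients in general. In Pain Units, where nearly all attenders may have pain, the factor is near 1.

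**Conclusion.** The conflict is real and should be resolved. The all-cancer denominator required by the primary objective can be formed only if sites disregard the literal wording of Section 7, Conduct, and of the visit description.

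The size is conditional. A general oncology site that enters only pain patients would overstate its all-cancer prevalence about 1.6- to 5.6-fold, if the Introduction's pain range applies there. The study-wide effect runs from none to that range, depending on how many sites read narrowly, and nothing in the documents says how many would. If all did, the register would hold 2,376 to 8,184 patients and give about ±2.0 to ±1.1 points at 50% instead of the stated ±1%.

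**What to change.** - Reconcile Protocol Sections 6.3 (both sentences), 7 (Conduct, Description of the visit and the later repeats) and 10.1 to one register rule that matches the objective: every adult cancer outpatient attending the investigator's consultation in the month, with or without pain. Delete third-step as a register condition.
- Add a yes/no register field for pain controlled with opioids, and list it in SAP Sections 5.1 and 5.2. Both the opioid-controlled-pain denominator and the all-cancer denominator can then be computed from the same register. State which of them is primary.
- Say in Section 9.5 that consent and the questionnaires belong to the characterisation part.
- If the SAP adds a sensitivity analysis without sites that entered no pain-free patients, do it within specialty, and do not drop Pain Units on that ground.

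The cost is a few sentences, one register field and a clarification letter to sites. Some sites will enter more short register lines. The change has to be in force before a site's prevalence month, because omitted patients cannot be recovered from the register afterwards.
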